Quantitative Analysis. Quantitative data from surveys and study databases will be summarized using descriptive statistics including frequencies, proportions, measures of central tendency (mean and median), and variability (standard deviation and interquartile range) along with data visualization methods, such as frequency tables, bar charts, line graphs, and scatter plots to understand implementation and effectiveness outcomes. 95% confidence intervals will be calculated when estimating proportions and means. Change from baseline to each post-intervention on effectiveness measures and mantram use will be calculated overall and by group (self-directed vs supported). Wilcoxon signed rank test and rank sum test will be used to examine the change in each group and compare the change between two groups. Linear mixed effects model will be used to examine the trajectory of change from baseline to post-intervention.

Qualitative analysis. Interviews will be recorded and transcribed. All qualitative data will be coded using a rapid qualitative data analytic approach. Unique and common themes across the two groups will be compared. Data analysis will be led by Drs. [name] and [name] and will also include qualitatively-trained members of the research team.

A matrix approach will be used to triangulate data from quantitative and qualitative sources. We will use a joint display analysis to support the integration of different data sources and types. Unique and common themes emerging across the two groups (self-directed and supported) will be identified and described.

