Sample size. As a feasibility study, the sample size was not projected to ensure enough study power for hypothesis testing. We assessed the effect size of the effectiveness measures (e.g., PCL-5) that can be detected with the planned sample size and 80% power. The effect size for change in outcome from baseline to post treatment in each intervention group and for overall was estimated based on a paired t-test. With a sample size of 20 per group and 40 in total, we could detect an effect size of 0.66 and 0.45, which are moderate effect sizes. To compare the outcome change between the self-directed and supported groups, we could detect a large effect size of 0.91 for the difference with 20 subjects per group. This effect size would be clinically meaningful thus signaling the need for additional study. The sample size assessment was also conducted for assessing feasibility measures (e.g., initiation rate). First, we assessed the precision of estimates based on projected sample size. We considered a range of target rate from 0.60 to 0.90 and estimated the width of the 95% exact binomial confidence interval for overall and for each intervention group. If an estimated intervention initiation rate is 0.80, a sample size of 40 (total) and 20 (per intervention group) will produce a two-sided 95% confidence interval with a width of 0.243 and 0.335, respectively. If an estimated intervention initiation rate is 0.90, the width of the 95% CI is reduced (becomes more precise) with the same sample size projected above.

BIBLIOGRAPHY AND REFERENCES CITED

- Almklov, E. Shi, S., Pittman, J.O.E., Heppner, P., Afari, N., [name], L. (submitted). Characterizing Veteran Responses on the Brief Personal Health Inventory to Inform Whole Health Care. *Psychological Services*.
- Bastien, C. H., Vallières, A., & Morin, C. M. (2001). Validation of the insomnia severity index as an outcome measure for insomnia research. *Sleep Medicine, 2*(4), 297–307.
- Blevins, C. A., Weathers, F. W., Davis, M. T., Witte, T. K., & Domino, J. L. (2015). The Posttraumatic Stress Disorder Checklist for DSM-5 (PCL-5): Development and Initial Psychometric Evaluation. *Journal of Traumatic Stress, 28*(6), 489–498.
- Borkovec, T. D., & Nau, S. D. (1972). Credibility of analogue therapy rationales. *Journal of Behavior Therapy and Experimental Psychiatry, 3*(4), 257–260.

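### The feasibility confidence-interval widths of 0.243 and 0.335 are described as exact binomial, but no exact interval tried gives them; they match the Wilson score interval

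*Combined protocol and SAP*

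**What the plan says.** The Sample size paragraph of the Data Analysis section ends with a precision assessment for feasibility measures, with the initiation rate as the example. On the rates covered it says: "We considered a range of target rate from 0.60 to 0.90". On the method, it says that the authors "estimated the width of the 95% exact binomial confidence interval for overall and for each intervention group".

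The next sentence gives the result for one rate. It opens "If an estimated intervention initiation rate is 0.80" and says that the total and per-group sample sizes "will produce a two-sided 95% confidence interval with a width of 0.243 and 0.335, respectively". The paragraph names no other interval method. It closes by saying that the interval is narrower at a rate of 0.90.

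The Quantitative Analysis paragraph of the same section says only that "95% confidence intervals will be calculated when estimating proportions and means". It does not say how the interval for a proportion will be computed.

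**The concern.** All inputs to the two widths are stated, so a reader should be able to reproduce them with the named method. That method gives wider intervals. If exact intervals are intended, the plan overstates its precision, more so within each group than overall. If another method was used, the description is wrong.

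These two widths are the only numerical statement of precision for the feasibility measures, and feasibility is part of Aim 1. The Sample size paragraph is also the only place that names an interval method for proportions. Because its figures contradict that name, an analyst cannot tell from the plan which interval to report.

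**Working it through.** **Inputs, all from the Sample size paragraph**

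- Confidence level: 95%, two-sided, so 0.025 in each tail and z = 1.95996 (z² = 3.8415).
- Rate: 0.80.
- Sample sizes: n = 40 in total and n = 20 per group. These give whole counts, x = 32 and x = 16, so rounding of counts cannot explain a gap.
- Printed widths: 0.243 and 0.335.

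**Step 1. The named method.** The Clopper-Pearson limits are the 0.025 quantile of Beta(x, n − x + 1) and the 0.975 quantile of Beta(x + 1, n − x).

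- 32/40: Beta(32, 9) and Beta(33, 8) give 0.6435 to 0.9095, width 0.2660.
- 16/20: Beta(16, 5) and Beta(17, 4) give 0.5634 to 0.9427, width 0.3793.

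Neither printed width is reproduced. The gaps are 0.266 − 0.243 = 0.023 (0.023/0.266 = 9%) and 0.379 − 0.335 = 0.044 (0.044/0.379 = 12%).

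**Step 2. Other readings of *exact*.** Clopper-Pearson is the usual meaning but not the only exact interval, and it is the most conservative of those tried here. Two shorter exact constructions were also computed:

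- Blaker: 0.253 and 0.350.
- Sterne type (inverting the exact test): 0.255 and 0.352.

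Both are still wider than the printed figures. The mid-P interval, which is only quasi-exact, gives 0.247 and 0.348. The Clopper-Pearson width averaged over a binomial count with rate 0.80 is 0.261 and 0.367.

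**Step 3. Where the printed figures come from.** The Wilson score interval without continuity correction has width

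2z · √[p(1 − p)/n + z²/(4n²)] / (1 + z²/n).

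- n = 40: p(1 − p)/n = 0.16/40 = 0.004000 and z²/(4n²) = 3.8415/6400 = 0.000600. The square root of 0.004600 is 0.06783. Width = 3.9199 × 0.06783 / 1.0960 = 0.2426.
- n = 20: 0.16/20 = 0.008000 and 3.8415/1600 = 0.002401. The square root of 0.010401 is 0.10198. Width = 3.9199 × 0.10198 / 1.1921 = 0.3354 (from unrounded values).

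Both round to the printed figures. The intervals are 0.6524 to 0.8950 and 0.5840 to 0.9193.

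| Method | Width, 32/40 | Width, 16/20 | Matches both? |
|---|---|---|---|
| Printed in the plan | 0.243 | 0.335 | – |
| Clopper-Pearson | 0.266 | 0.379 | No |
| Blaker | 0.253 | 0.350 | No |
| Sterne type | 0.255 | 0.352 | No |
| Wilson score | 0.243 | 0.335 | Yes |
| Wilson, continuity-corrected | 0.265 | 0.377 | No |
| Jeffreys | 0.243 | 0.337 | No |
| Wald | 0.248 | 0.351 | No |
| Agresti-Coull | 0.248 | 0.347 | No |

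**Step 4. The claim about a rate of 0.90.** The Clopper-Pearson widths there are 0.209 (36/40) and 0.305 (18/20), and the Wilson widths are 0.191 and 0.273. The interval does narrow under either method, so that sentence is correct.

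**The case against.** The strongest reply is that nothing was miscalculated. Both printed figures are correct Wilson widths to three decimals, and Wilson is a valid interval for a proportion. The word *exact* stands in the sentence about the range of rates, while the sentence with the figures mentions only a two-sided 95% interval. On this view one adjective is wrong, and it has almost no consequence. The paragraph says the sample size was not chosen for hypothesis-testing power. It sets no precision target and ties no decision to a confidence limit. The lower limit would move only from 0.652 to 0.644 (n = 40) and from 0.584 to 0.563 (n = 20). The silence of the Quantitative Analysis paragraph on method contradicts nothing.

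Much of this stands. A wrong label is the likeliest explanation, and the consequence is small. The separation into two sentences does not help much: the second sentence reports the result of the assessment described in the first, and no other method is named between them. As written, the method and the numbers disagree, and only the authors can say which they meant. The missing method in the Quantitative Analysis paragraph is not itself an error. Naming one there is a consistency step, and it does not carry the point.

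**Conclusion.** The point holds and is minor. The method named in the Sample size paragraph does not produce the widths printed there. Under Clopper-Pearson they are 0.266 and 0.379 instead of 0.243 and 0.335. If the exact method is meant, both printed figures are too favourable, by 0.023 overall and 0.044 per group. If Wilson is meant, the figures are right and only the description is wrong.

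This rests on the stated rate of 0.80, the stated sample sizes, and full two-sided 95% widths. It does not depend on reading *exact* as Clopper-Pearson, since the Blaker and Sterne-type intervals also fail to give the printed figures. That Wilson was the method used is an inference from the match at both sample sizes; the plan does not say so. The sample size of 40 is unaffected.

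**What to change.** In the Sample size paragraph, make one of two changes:

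- keep the exact binomial method and restate the widths as 0.266 (n = 40) and 0.379 (n = 20); or
- keep 0.243 and 0.335 and describe the interval as the Wilson score interval.

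Then name the chosen method in the Quantitative Analysis paragraph for confidence intervals for proportions, so that the reported intervals match the planning figures.

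Optionally, because rates down to 0.60 were considered, add the widths at 0.60, where the intervals are widest within that range: 0.318 and 0.448 for Clopper-Pearson (24/40 and 12/20), or 0.291 and 0.395 for Wilson.

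The cost is one label or two numbers, plus one method name. No participants are added and the design does not change.
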